## 8 **Statistical analysis plan**

9 Outcomes will be analyzed using the modified intention-to-treat (mITT) strategy. The mITT  
10 population will consist of all participants with randomly assigned surgery and have available  
11 at least a year of postoperative data from 1 to 3 years. Baseline and operation-related  
12 characteristics of the LN and LP groups will be compared using independent t-tests for  
13 continuous variables, and chi-square tests or Fisher's exact tests for categorical variables.  
14 Postoperative clinical outcomes and radiological parameters will be compared between  
15 groups and over time using linear mixed-effects models, with fixed effects including  
16 preoperative values of tested variables, group, time, interaction between group and time,  
17 other factors with possible relation with outcomes such as age, BMI and disease, and a  
18 random effect of subjects. Least squares mean for postoperative clinical outcomes and  
19 radiological parameters will be estimated. Comparisons will be made between the treatment  
20 groups. For variables with a significant difference in the interaction between time and group,  
21 post-hoc analysis will be performed for each time point and adjusted p-values will be  
22 evaluated using the Bonferroni method. All data will be analyzed using SPSS software  
23 version 27.0 (SPSS, Chicago, IL, USA), with statistical significance defined at  $p < 0.05$  (two-  
24 sided).

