1

2

3

4

5     **Title: Randomized Controlled Trial Comparing Clinical and Radiological Outcomes**  
6       **Between C3 Laminectomy with C4-C6 Laminoplasty and C3-C6 Laminoplasty**

7

8       **Study protocol (date: 2017-01-05)**

9

1 **Background**

2 C3 laminectomy in cervical laminoplasty is a modified laminoplasty technique that can  
3 preserve semispinalis cervicis muscle attached to the C2 spinous process. Several previous  
4 studies have shown that this technique can lead to better outcomes of postoperative axial neck  
5 pain and C2-C3 range of motion (ROM) than conventional cervical laminoplasty. However,  
6 there is still a lack of understanding of total and proportional postoperative cervical sagittal  
7 alignment outcomes.

8

9 **Study design**

10 A randomized clinical trial will be conducted on patients with cervical laminoplasty for  
11 treating CSM or OPLL at a single tertiary referral university hospital. Patients will be  
12 randomly assigned to either the LN group (C4-6 laminoplasty with C3 laminectomy) or the  
13 LP group (C3-6 laminoplasty) at a 1:1 ratio. The sample size will be calculated to achieve a  
14 target of 80% power with a two-tailed significance level of 0.05, with a medium effect size  
15 (Cohen's  $d = 0.50$ ), resulting in 63 patients per each group. The trial will enrolled consecutive  
16 patients who underwent cervical laminoplasty from March 2017. Participants' ages will  
17 ranged from 20 to 80 years. Patients with metastatic tumors, combined fractures, or previous  
18 posterior cervical surgeries will be excluded from this study. Patients with a diagnosis of  
19 CSM or OPLL will be assessed prior to randomization by a neurosurgical specialist through a  
20 combination of history-taking, clinical examination, and radiological workup, including  
21 dynamic radiographs and cervical spine computer tomography (CT) or magnetic resonance  
22 image (MRI) scans. Diagnosis of CSM will be based on symptoms of myelopathy and  
23 stenosis at two or more cervical levels on MRI. Diagnosis of OPLL will be made based on  
24 CT findings. The randomization process, surgical group options, and required follow-up  
25 evaluations and imaging will be fully explained to eligible patients by a neurosurgical

1 specialist. After obtaining informed consent, patients will be randomized using a computer-  
2 generated block design in 1:1 ratio with concealed assignment managed by an independent  

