3 research nurse. The attending surgeons, patients, and staff members in the operating room  
4 will be blinded to the surgical method until the day of surgery. A concealed paper indicating  
5 the patient's assigned group will be provided in the operating room, and the surgeon will  
6 verify the patient's group just before commencing the surgery. This study was approved by  
7 the hospital's Institutional Review Board (IRB number: H-1610-136-804).

8

9 **Data collection and outcomes**

10 Data will be collected using patient-reported outcome questionnaires and plain x-rays taken at  
11 the outpatient clinic before surgery and at 1, 2, and 3 years postoperatively. Patients will  
12 record their outcomes directly without assistance of the surgeon or other study participants.  
13 Radiological parameters will be assessed using 150% magnified images by one of the authors  
14 (a fellow). Three measurements will be performed, and the median value will be selected as  
15 the final measurement. The measurements will be conducted utilizing the measuring tools  
16 within the institution's Picture Archiving and Communication System (M6, Infinit  
17 Healthcare, Seoul, Korea) operating on a Microsoft Windows environment (Microsoft Corp.,  
18 Redmond, WA, USA). We selected C2-C7 Cobb angle (C2-C7 CA) as the primary outcome  
19 measure, considering the importance of postoperative kyphotic changes in cervical  
20 laminoplasty, which have been associated with long-term recurrent myelopathy and chronic  
21 neck pain. Additionally, we chose the Neck Disability Index (NDI) as another primary  
22 outcome measure to evaluate axial neck pain, as it is commonly acknowledged as a potential  
23 advantage of C3 laminectomy. Secondary outcome measures included other radiologic  
24 parameters such as C2-C3 Cobb angle (C2-C3 CA), C4-C7 Cobb angle (C4-C7 CA), cervical  
25 sagittal vertical axis (cSVA), T1 slope (T1S) and T1 slope minus cervical lordosis (T1S-CL),

1 as well as presence of C2-C3 interlaminar fusion. Other clinical outcomes, such as numerical  
2 rating scores for neck (NRS-N) and limb (NRS-L) and the Euro-Quality of Life-5 Dimension  
3 (EQ-5D), will be also assessed. We will examine operation-related factors, including open  
4 side, presence of dome-like laminectomy at the C2 or C7 level, operative time, estimated  
5 blood loss, and complications such as hinge fracture, neural injury, dural injury, and wound  
6 infection.

7

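### The listed mixed model has no preoperative value × time term, so the year-3 arm difference and the gating group × time test can be biased if the baseline effect changes over time and baseline-dependent follow-up differs between arms

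*Combined protocol and SAP*

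**What the plan says.** The Statistical analysis plan compares postoperative outcomes between "groups and over time using linear mixed-effects models, with fixed effects including" the terms "preoperative values of tested variables, group, time, interaction between group and time". It adds further covariates, for which age, BMI and disease are given as examples, and a random subject effect. Group × time is the only interaction named.

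The section then announces comparisons between the treatment "groups. For variables with a significant difference in the interaction between time and group", and says that Bonferroni-adjusted tests at each time point follow for those variables. The interaction test is therefore the gate to the yearly comparisons.

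Under Data collection and outcomes, measurements are taken at "the outpatient clinic before surgery and at 1, 2, and 3 years postoperatively". The modified intention-to-treat set needs "at least a year of postoperative data from 1 to 3 years", so patients with one, two or three postoperative visits can all contribute. The document gives no dropout rate, no missing-data assumption and no correlation between preoperative and postoperative values by year.

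**The concern.** With a single coefficient, the preoperative value is made to predict the 1-year and 3-year outcomes equally strongly. If its true influence changes over the three years, the pooled coefficient adjusts too much in one year and too little in another. The misfit is harmless while the arms have the same preoperative mix among the patients observed at each visit. If that mix drifts apart between arms as patients are lost, the misfit enters the year-specific arm differences with a size that varies by year, and so looks like a group × time interaction.

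Two results are exposed for both primary outcomes (C2-C7 Cobb angle and NDI): the year-3 difference, and the test that opens the yearly comparisons. The flaw lies in the mean model and is separate from the choice of residual covariance.

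**Working it through.** **1. The plan's own figure.** Study design aims for a "target of 80% power with a two-tailed significance level of 0.05, with a medium effect size" (d = 0.50), "resulting in 63 patients per each group". Check: n = 2(z₀.₉₇₅ + z₀.₈₀)²/d² = 2(1.960 + 0.842)²/0.25 = 62.8, so 63 per arm, with 80.1% power by the normal formula. The exact noncentral t gives 79.5% at 63 and asks for 64. The stated figure is reproduced.

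**2. Mechanism.** Let β_t be the true slope on the preoperative value at year t, β̄ the pooled slope, and Δ_t the arm difference in mean preoperative value among patients observed at year t. The error in the year-t arm difference is approximately (β_t − β̄) × Δ_t. It is zero if the slope is constant. It is zero on average if Δ_t is zero on average, which covers complete data after randomisation and dropout that depends on baseline in the same way in both arms.

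Check with complete data, slopes 0.8/0.5/0.2 (β̄ = 0.5) and a fixed imbalance of 0.2 SD. Year 1: 0.3 × 0.2 = +0.060. Year 2: 0. Year 3: −0.3 × 0.2 = −0.060. Simulation (1500 trials) gave +0.062, 0.000 and −0.059, with the interaction rejected in 5.7%. With dropout, the random intercept borrows from earlier visits, so the formula is only a guide and simulation is needed.

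**3. Simulation A (assumed inputs).** 63 per arm, no true arm effect, preoperative value standardised to SD 1, residual variance 0.75, within-patient correlation 0.5, REML random-intercept model, 2000 trials per scenario. Retention in the dropout rows is about 95/85/70% at years 1/2/3. Monte Carlo standard error is about 0.004 for a bias, and √(0.05 × 0.95/2000) = 0.5 percentage points for a 5% rejection rate. Year-3 bias and interaction rejection with the common slope:

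| Follow-up depends on baseline | Constant slope 0.5 | Fade 0.6/0.45/0.3 | Fade 0.8/0.5/0.2 |
|---|---|---|---|
| Complete data | 0.000; 5.3% | 0.000; 5.1% | −0.001; 5.8% |
| Same in both arms | 0.000; 4.6% | −0.001; 4.6% | −0.002; 5.2% |
| One arm only | 0.001; 4.8% | −0.054; 5.4% | −0.106; 7.4% |
| Opposite in the two arms | 0.001; 5.3% | −0.109; 8.2% | −0.215; 17.2% |

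- Bias at years 1 and 2 was at most 0.012 throughout.
- A false interaction followed by at least one Bonferroni-significant year occurred in 1.2% and 2.7% of trials (one arm, the two fades) and 2.4% and 7.2% (opposite), against 1.0 to 1.1% with preoperative value × time.
- With that term, bias was at most 0.003 and interaction rejection 4.8 to 5.3% in every scenario.
- Units are preoperative SDs. The year-3 outcome SD is √(0.3² + 0.75) = 0.917 or √(0.2² + 0.75) = 0.889, so on that scale the biases are 9 to 13% larger.

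**4. Simulation B.** Slopes 0.8/0.65/0.5 or 0.8/0.7/0.6, residual correlation 0.6, 24 to 27% missing at year 3, opposite dependence, 1000 trials per scenario. Year-3 bias was 0.056 and 0.120 on an outcome SD of 0.78 (0.07 and 0.15 SD), and 0.043 and 0.080 on 0.85 (0.05 and 0.09 SD). Interaction rejection was 7.6%, 15.9%, 6.1% and 8.7%. With the extra term, bias was at most 0.005 and rejection 4.1 to 5.8%. Same-direction dropout with the common slope: bias −0.005, rejection 4.7%.

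**5. Simulation C.** Slopes 0.8/0.65/0.5, covariance treated as known, 600 trials. One-arm dropout gave a year-3 bias of about 0.04 outcome units and 11% rejection (Monte Carlo standard error √(0.11 × 0.89/600) = 1.3 points). Opposite dropout gave about 0.10 and 16%. With the extra term, bias was at most 0.007 and rejection about 4 to 6%.

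**6. Difference averaged over years.** Slopes as in B, 25 to 27% missing at year 3, known covariance, 1500 trials. Bias was 0.027 to 0.035 (opposite), 0.010 to 0.019 (one arm) and 0.004 (same direction), against a sampling SD of about 0.095. Rejection was 4.9 to 6.8%.

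**7. Precision.** With complete data and the slopes in B, the common-slope model has standard errors about 1 to 3% larger at years 1 and 3. In A's strongest fade the sampling SDs are 0.165 against 0.155 and 0.162 against 0.154, or 5 to 6% larger.

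**The case against.** The strongest reply is that no stated premise makes the bias likely. The document does not say that the preoperative value loses influence, and the first postoperative visit is already at year 1, so any change must occur between years 1 and 3. With a constant slope, no dropout pattern tested produced bias. Both arms undergo laminoplasty, differ in how C3 is handled, and share one visit schedule; nothing suggests that patients would be lost in opposite ways. A single baseline slope is a common ANCOVA-type choice, and because the list of fixed effects is introduced as open, the term is unlisted rather than excluded. All of this stands, and it limits the priority.

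It does not remove the point. Partial follow-up is expressly admitted, blinding is promised only up to the day of surgery, and an open list lets the term be decided after the data are seen.

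Two stronger readings are tempting and are not supported:

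- A reader might infer that a fading baseline effect plus baseline-related dropout is enough for bias. It is not: when the dependence is the same in both arms, the misfit cancels.
- A reader might infer that any baseline imbalance produces a false interaction. With 63 per arm, the standard error of a baseline difference is √(2/63) = 0.178 SD, so an imbalance of 0.2 SD or more arises by chance in about 26% of trials. The resulting error is conditional on that trial and averages to zero over randomisations. Rejection stayed at 5.1 to 5.8% for fading slopes with complete data.

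**Conclusion.** The point holds in a limited form. As listed, the model leaves the year-3 arm difference and the gating interaction test open to bias if the baseline effect changes over time and baseline-dependent follow-up differs between arms.

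In the milder one-arm case the year-3 bias is roughly 0.05 to 0.11 SD. That is about 11 to 21% of the design effect of 0.50 (0.054/0.50 and 0.106/0.50), against a standard error near 0.18 SD. Interaction rejection is about 5 to 11%; the upper figure comes from the small known-covariance run. In the extreme opposite-direction case, bias is roughly 0.05 to 0.2 SD and rejection about 6 to 17%.

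Every size rests on assumed slopes, retention and dropout strength, because the document supplies none. The results do not show that the ungated treatment comparison is unsound, nor that the sample size is wrong. This is an inexpensive safeguard of low-to-moderate priority.

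**What to change.** In the Statistical analysis plan, add preoperative value × time, with time as a three-level factor (years 1, 2 and 3), to the fixed effects of every longitudinal model, and fix this before the outcome data are analysed. State that least squares means are evaluated at the overall preoperative mean. The arm differences do not depend on that choice, because the model has no group × preoperative value term.

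The cost is one term in the SPSS mixed-model specification and two degrees of freedom. It needs no new data, and 63 per arm is unchanged. If the slope is in fact constant, the precision cost is small: in simulation A the year-3 sampling SD went from 0.153 to 0.154 with complete data, and from 0.175–0.176 to 0.178–0.182 with dropout (about 1 to 4%).

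### The mixed model names only a subject random effect and no residual covariance for years 1, 2 and 3; if spread or correlation changes over time, the year-specific intervals and the gating interaction test can be miscalibrated

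*Combined protocol and SAP*

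**What the plan says.** Under Data collection and outcomes, measurements are taken at "the outpatient clinic before surgery and at 1, 2, and 3 years postoperatively", so each patient contributes up to three post-operative values. Both primary outcomes, C2-C7 Cobb angle and NDI, follow this schedule.

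Under Statistical analysis plan, the model is a linear mixed-effects model. Its fixed effects are "preoperative values of tested variables, group, time, interaction between group and time", plus factors such as age, BMI and disease. The random part appears in the run "random effect of subjects. Least squares mean for postoperative clinical outcomes and". The plan names no random slope, residual covariance structure, robust standard error or missing-data sensitivity analysis.

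Where the interaction is significant, "post-hoc analysis will be performed for each time point and adjusted p-values will be" obtained by the Bonferroni method. The mITT set admits patients who have only part of the year 1 to 3 data.

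**The concern.** One random intercept per subject with independent residuals implies compound symmetry: equal variance at years 1, 2 and 3, and the same correlation between years 1 and 3 as between adjacent years. Three-year alignment and disability scores need not behave like that.

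Two features of the plan lean on the assumption:

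- **Year-specific tests.** The interaction test opens the post-hoc step. If the year-specific contrasts come from the same model, they use a standard error pooled over visits. If spread grows, that error is too large early and too small late.
- **Incomplete follow-up.** When dropout depends on earlier results, a likelihood analysis recovers the group difference only if its covariance is adequate.

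At stake are the p-values and confidence intervals by year for both primary outcomes.

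**Working it through.** **Inputs from the documents.** Three post-operative visits; two-sided 0.05; "target of 80% power"; d = 0.50; "resulting in 63 patients per each group"; 1:1 allocation. Three post-hoc tests give a Bonferroni level of 0.05/3 = 1.67%, critical value 2.394.

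**Inputs not in the documents, therefore assumed.** SD by year (after adjustment for the fixed effects), correlation between years, and dropout.

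**1. The plan's own figure.** n = 2(1.960 + 0.842)²/0.50² = 62.8, so 63 per group. It reproduces. (With the noncentral t, power at 63 is 79.5%.) Nothing below changes it.

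**2. Year-specific standard errors, complete data.** The random-intercept fit replaces the three variances by their mean, so

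model SE / true SE at visit t = √(mean variance / variance at t), and test size = 2[1 − Φ(z × ratio)].

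For SDs 0.8/1.0/1.2 the mean variance is (0.64 + 1.00 + 1.44)/3 = 1.027. The ratios are √(1.027/0.64) = 1.27, √(1.027/1.00) = 1.01 and √(1.027/1.44) = 0.84. Year-3 size at the Bonferroni level is 2[1 − Φ(2.394 × 0.844)] = 4.3%.

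| Assumed SDs, years 1/2/3 | SE ratio, years 1/2/3 | Year-3 test alone, nominal 1.67% |
|---|---|---|
| equal | 1.00/1.00/1.00 | 1.67% |
| 0.9/1.0/1.1 | 1.11/1.00/0.91 | 2.9% |
| 1/1.15/1.3 | 1.16/1.01/0.89 | 3.3% |
| 0.8/1.0/1.2 | 1.27/1.01/0.84 | 4.3% |

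The correlation does not enter this formula. Unequal correlation alone leaves these standard errors exact.

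**3. Interaction test.** Take equal SDs and correlations 0.7 for adjacent years and 0.49 for years 1-3. The mean correlation is (0.7 + 0.7 + 0.49)/3 = 0.63, and the SE ratio for the year 3 minus year 1 contrast is √[(1 − 0.63)/(1 − 0.49)] = 0.85. The interaction test then has size 5.5%. With correlations 0.8 and 0.4 the ratio is √[(1 − 0.667)/(1 − 0.4)] = 0.75 and the size 7.3%.

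**4. Overall comparison.** The variance of a patient's three-visit average is (sum of variances + 2 × sum of covariances)/9. The random-intercept fit preserves both sums, so the ratio is 1. In simulation the size was 4.8-5.0% in all nine scenarios tried.

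**5. Full path: significant interaction, then any Bonferroni visit.** Simulated trials, 63 per arm, complete data, AR(1) correlation, no effect at any visit:

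| SDs | Random intercept | Unstructured |
|---|---|---|
| 0.8/1.0/1.2 | about 2% | about 1% |
| 0.7/1.0/1.3 | about 3% | 1.1-1.3% |

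With SDs 0.8/1.0/1.2 and no gate, the chance of any significant Bonferroni visit was 4.9-5.4%. With a true effect of 0.5 at year 1 only (AR(1) 0.7), gated false positives at year 3 were 3.2%, against the 1.67% per-visit share.

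**6. Dropout depending on the previous year's result.** 200,000 simulated patients per arm, 71-80% still observed at year 3. Bias of the year-3 group difference, in year-1 SD units:

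| Situation | Random intercept | Unstructured |
|---|---|---|
| true covariance is compound symmetric | about 0 | about 0 |
| same rule in both arms, no effect | about 0 | about 0 |
| same rule in both arms, d = 0.5 | −0.02 to +0.01 | about 0 |
| opposite rules by arm | −0.04 to +0.10 | at most 0.01 in size |

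**The case against.** The strongest reply is that nothing in the documents shows the assumption to be false. They give no SD by year, correlation or dropout rate. SDs of 0.8/1.0/1.2 mean a 2.25-fold rise in variance (1.44/0.64) after adjustment for the preoperative value. Stable spread would remove the year-specific error, and shrinking spread would reverse it. This stands, and every size given here is conditional on it.

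A second reply is that silence is not a rule. The plan does not say that the subject effect is the only covariance term, nor that the post-hoc contrasts use the model's pooled error; separate analyses by visit would escape the standard-error argument. This also stands, but a primary analysis should not leave either choice open until the data are seen.

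A third reply is that the decision path is protected. A reader might infer a type I error near 10%, since 2[1 − Φ(1.96 × 0.844)] = 9.8%. That figure belongs to an ungated, unadjusted year-3 test, which the plan never performs. Under no effect the gate and Bonferroni keep the path below 5%. The protection is weaker once a real early difference opens the gate, and it does nothing for the confidence intervals.

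**Conclusion.** The plan leaves the residual covariance unstated. Read as written, it assumes equal variance and equal correlation over years 1 to 3. If variance changes with time, year-specific standard errors and intervals are miscalibrated: under the assumed growing spreads they are 11-27% too large at year 1 and 9-16% too small at year 3. If correlation decays, the gating interaction test is slightly anti-conservative, at about 5.5-7%.

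The documents do not support the stronger inference that the year-specific standard errors are wrong and the estimates biased as such. With equal SDs those standard errors are exact on complete data. Dropout bias is about 0 to 0.02 SD if the rule is the same in both arms, and reaches about 0.1 SD only if it differs by arm, against a design effect of 0.50 SD. The overall group comparison on complete data and the sample size of 63 per group are unaffected. This is a worthwhile, inexpensive improvement, and the overall error rate under no effect is not at risk from it.

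**What to change.** In the Statistical analysis plan, replace the subject random effect with an unstructured 3x3 residual covariance over the year 1, 2 and 3 visits (in SPSS MIXED, REPEATED visit with COVTYPE(UN)), using Satterthwaite or Kenward-Roger degrees of freedom. Keep the stated fixed effects. Name one fallback in advance for non-convergence: heterogeneous AR(1). State that the overall and year-specific least squares mean differences both come from this model. Letting the preoperative value interact with visit is optional and not part of this change.

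The cost is one line of syntax and a short addition to the SAP. The covariance has six parameters instead of two, so four more, which 2 × 63 = 126 patients with up to three visits each can support. The remaining downside is a small risk of non-convergence, which the fallback covers.

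### The plan does not define the Bonferroni family for the year-by-year tests: within a visit nothing is adjusted; over three visits it is valid, and Holm would do slightly better

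*Combined protocol and SAP*

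**What the plan says.** Under Study design, patients are "randomly assigned to either the LN group (C4-6 laminoplasty with C3 laminectomy) or the" "LP group (C3-6 laminoplasty) at a 1:1 ratio", so there are two arms. The sample size rests on a "target of 80% power with a two-tailed significance level of 0.05, with a medium effect size" of Cohen's d = 0.50, "resulting in 63 patients per each group". Under Data collection and outcomes, data are collected at "the outpatient clinic before surgery and at 1, 2, and 3 years postoperatively".

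Under Statistical analysis plan, the mixed model's fixed effects include "preoperative values of tested variables, group, time, interaction between group and time". The baseline value is a covariate, so years 1, 2 and 3 are the outcome visits. Where the interaction is significant for a variable, "post-hoc analysis will be performed for each time point and adjusted p-values will be" "evaluated using the Bonferroni method. All data will be analyzed using SPSS software". No multiplier is given, and nothing says whether the adjustment runs within a visit, across the three visits, or over comparisons between visits within an arm.

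**The concern.** With two arms, each visit offers exactly one LN-LP contrast. A Bonferroni correction confined to a visit therefore multiplies by 1, and p-values labelled as adjusted would be raw. A correction across the visits multiplies by 3. Two analysts could both follow the text and report year-specific p-values that differ threefold, and the choice could be made after the results are known.

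This matters because the rule decides at which years the arms are said to differ. It covers both primary outcomes (C2-C7 Cobb angle and NDI) and the secondary outcomes analysed with the mixed model. A second, smaller point is that even the protective reading uses a method that Holm's procedure matches or beats under the same assumptions.

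**Working it through.** **Inputs from the documents.** Two arms, 1:1; 63 per arm; d = 0.50; two-sided alpha 0.05; three postoperative visits; yearly tests only after a significant interaction.

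**Inputs assumed.** The documents give no between-visit correlation and no pattern of effect over time. I take equal variances, one common correlation r between visits (0.5 and 0.7), and the effect patterns shown below in SD units. There are no missing data.

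**Step 1: the plan's own figure.** n per arm = 2(1.960 + 0.842)² / 0.50² = 62.8, so 63. Power at 63 is Φ(0.50/√(2/63) − 1.960) = Φ(2.806 − 1.960) = 80.1%. The plan's figure is reproduced under the normal approximation. It is a single-contrast calculation and is not affected by this point.

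**Step 2: multipliers and thresholds.**
- Within a visit: 1 contrast, multiplier 1, threshold 0.05.
- Bonferroni over three visits: 0.05/3 = 0.0167 for every visit.
- Holm over three visits: smallest p against 0.0167, next against 0.025, largest against 0.05, stopping at the first failure.

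The smallest p-value faces 0.0167 under both three-visit methods. Holm can therefore differ only at the second and third smallest.

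**Step 3: simulation.** The three visit contrasts z₁, z₂, z₃ are normal with means d/√(2/63), variance 1 and correlation r. The interaction is significant when Σ(z − z̄)²/(1 − r) exceeds 5.99 (2 df, 0.05). Yearly tests count only if it does. There were 300,000 or more replicates per scenario.

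**Step 4: false findings.** Three unadjusted tests with no interaction test have a family-wise error of 1 − 0.95³ = 14.3% if independent. With no effect at any visit, the interaction test holds the unadjusted rate to 1.6-4.3% (r from 0.7 to 0). It does not do so when one year truly differs. With an effect of 0.5-0.6 SD at year 3 only and r = 0.5-0.7, the chance of a significant interaction plus a false difference at year 1 or 2 is:

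| Adjustment | Chance |
|---|---|
| Within a visit (none) | 7.5-8.5% |
| Bonferroni over three visits | 2.6-2.9% |
| Holm over three visits | 3.3-3.9% |

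**Step 5: power, Bonferroni over three visits against Holm.** These are the chances that the interaction is significant and the year is then declared different (years 1/2/3), at r = 0.7:

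| True effects (SD) | Interaction significant | Bonferroni | Holm | At least one year, either method |
|---|---|---|---|---|
| 0.2/0.35/0.5 | 48% | 2.5/16.2/37.0% | 5.1/18.8/37.2% | 37.8% |
| 0.3/0.5/0.6 | 49.5% | 6.8/33.6/44.2% | 12.7/35.9/44.7% | 45.6% |

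The largest gain is 12.7 − 6.8 = 5.9 points; the others are under 3. At r = 0.5 the interaction is significant in about 31% of trials and every gain in these two patterns is under 3 points. With effects 0/0.5/0.5 at r = 0.5, each affected year goes from 57.8% to 60.5%. With d = 0.5 at all three years, the interaction is significant in only 5% of trials and Holm adds about 0.3-0.4 points per visit.

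**The case against.** The strongest reply is that a within-visit correction would be pointless with two arms, so a sensible reader takes Bonferroni to run across the three visits. On that reading the plan is valid, prespecified and below 5%, and preferring Holm is a matter of efficiency. This largely stands. A reader might infer that the plan leaves its yearly claims unprotected. The text does not support that: it says the tests are done visit by visit, not that each visit is its own family. The 7.5-8.5% belongs to one possible reading. The text does not exclude that reading either, and comparisons over time within an arm are a third possibility.

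A reader might also infer a large power loss. Among trials with a significant interaction, year 1 in the 0.3/0.5/0.6 pattern rises from 6.8/49.5 = 14% to 12.7/49.5 = 26%. But the interaction is significant in only about half of such trials, so the gain in what the trial would actually report is about 6 points, and it is the largest found.

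Finally, Holm and Bonferroni share the nominal 0.05 bound but not the achieved error. Under partial nulls Holm uses more of the bound (3.3-3.9% against 2.6-2.9% above), so part of its gain comes from there.

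**Conclusion.** The gap is real: the Bonferroni family is undefined, and one available reading adjusts nothing. Under that reading, a true difference at year 3 alone carries about a 7.5-8.5% chance of a significant interaction plus a false difference at an earlier year, against the plan's 5% level. Under the across-visit reading nothing is invalid. Holm never rejects less and gains about 0-6 points per visit in the assumed scenarios, only at the second and third smallest p-values, with no change in the chance of at least one significant year.

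All these sizes rest on the assumed effect patterns, the assumed correlation and equal variances over visits. The sample size, the mixed model and the overall group comparison are untouched. Minor priority.

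**What to change.** Replace the Bonferroni wording with:

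> For each outcome the three LN-LP contrasts at 1, 2 and 3 years form one family; their raw p-values are Holm-adjusted across the three years, with unadjusted 95% confidence intervals shown.

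Compute the adjustment from the three raw p-values, not from an option that adjusts within a visit. The cost is one sentence and a three-number calculation, with no extra patients, visits or data. The downside is that Holm has no simple matching simultaneous intervals, so an unadjusted interval may exclude zero where the adjusted p-value is not significant.

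If the sponsor prefers Bonferroni, naming the same three contrasts as the family closes the gap by itself; Holm is the small further gain.
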